collected: age, gender, nationality (German or non-German), main diagnosis according to International Classification of Diseases, 10th Revision groups (cancer/chronic heart disease/lung disease/others), frequency of using electronic devices, type of electronic device (personal computer, notebook, tablet, smartphone, etc), and operating system (Windows, Apple, Android, etc). Furthermore, the research team will measure the time (in minutes) that participants need to complete each IPOS version. After completing the electronic and the paper IPOS, the researcher will ask patients which version they prefer.

Sample size calculation

With a power of 80%, a target ICC of 0.9 and a significance level of $\alpha=0.05$, the calculated sample size is 47. Considering possible drop-outs, it is planned to include 50 participants.

Data analysis

A two-way ICC model with fixed effects will be calculated.³⁴ The Wilcoxon test will be used for comparing IPOS values of both versions and completion time. Equivalence will be established for individual IPOS items, for IPOS subscales (physical symptoms subscale, emotional concerns, communication and quality of care subscale)¹⁷ and the total IPOS score. Bland-Altman plots will be created to present the equivalence and differences between both versions visually for IPOS subscale values and the IPOS total score. To judge the amount of sampling bias, the sociodemographic details of participants will be compared with population profiles of participating sites via descriptive statistics.

Data from substudy II will inform the development of a valid and reliable eIPOS that can be implemented into routine clinical care to be tested in MRC phase 2 of this study.

Feasibility/piloting (MRC phase 2)

MRC phase 2 of this project focuses on testing procedures of the intervention (piloting), estimating recruitment/retention rates and determining the acceptability of the intervention (feasibility). Phase 2 consists of two parts (figure 1 for details of the integration within the overall study design): the intervention and implementation procedures developed in phase 1 will be tested (substudy III). Furthermore, the acceptability of the intervention will be determined using a qualitative approach (substudy IV).

Substudy III: quasi-experimental study to pilot and test the feasibility of the eIPOS intervention

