eIPOS, electronic Integrated Palliative care Outcome Scale; SPHC, specialised palliative home care.

Intervention group

At baseline, a study nurse will introduce the patient to eIPOS. After that, the participant will complete eIPOS every 3 days. There will be no obligation to answer each item of the eIPOS. Standardised procedures (for example: frequency of measurement, time point of introduction) will be finalised after phase 1. The information from self-reported eIPOS will be used in routine care processes of the service.

Prospective control

All patients who are cared for by one of the participating SPHC teams, but do not use the eIPOS, will serve as a control group. No additional interventions are planned for this group. However, care processes for this prospective control group might change because of staff being introduced to training around outcome measurement.

Retrospective control

A retrospective chart review will be conducted to provide information on care processes in the services before the introduction of a self-report PRO measure.

Inclusion criteria

The inclusion criteria are similar to substudy I and summarised in [table 2](#).

Recruitment

Intervention group: patients will be recruited from each participating team with the support from a study nurse. A study nurse will inform eligible patients in detail about the aims, study procedure and requirements. If the patient is interested, the study nurse will make an appointment for the introduction of the electronic system and perform the baseline assessment. The patient will need to give written consent before participation.

Outcome measures

Recruitment as well as drop-out rates, technical feasibility (completeness of each eIPOS) and the influence of eIPOS on provided care will be measured as the primary outcomes of interest.

Secondary outcomes will include change in palliative concerns, quality of life and symptom burden measured

with the eIPOS, the EORTC QLQ-C15-PAL (measuring health-related quality of life of palliative patients with cancer)³⁵ and the Edmonton Symptom Assessment Scale (assessing symptoms of palliative care patients)³⁶ at baseline and after 2 weeks.

Data extracted from medical records for both the intervention and control groups will include the number and severity of palliative symptoms and concerns and the steps taken by professionals for reducing the symptoms. Additionally, the number of unplanned hospital admissions will be collected.

Sample size calculation

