In this study, the research team will work with a variety of stakeholders to consider different requirements, perspectives and opinions in this very challenging research setting. A mixed-methods approach was chosen to explore different barriers and facilitators of the planned intervention.

Recruitment is a natural challenge in the palliative care setting. Even more so, patients eligible for SPHC suffer from life-limiting diseases with a complex symptom burden. Developing a rapid process for the identification and inclusion of eligible patients with the participating SPHC teams as well as the fact that all study appointments will take place in the patients' home should increase the recruitment rates for all study parts. A limitation of the study is its convenience sample based on staff identification of eligible patients in participating study sites. Therefore, gatekeeping and sampling of only comparatively fitter patients cannot be ruled out completely. We hope to mitigate this sampling bias by training staff and co-designing the intervention with staff from the participating sites. We will compare the sociodemographic details of recruited patients with population data from the services to quantify this possible bias.

The use in clinical practice will depend on the compliance with the newly developed intervention.⁴⁰ Other researchers, for instance, Lang *et al*⁴¹ explored non-compliance with a telemedical intervention for multimorbid patients over 65 years and discovered that missing additional benefits of the intervention, missing content variety and no interest in telemedical care were the main reasons for drop-outs and/or not using the intervention at all. Studies with patients suffering from heart failure or chronic obstructive pulmonary disease testing telemedical interventions have a drop-out rate of around 20% and almost one-third of the patients refuse to participate.⁴²

Therefore, the involvement of patients and professionals is crucial in the development and implementation of eIPOS. In phase 1, barriers and facilitators of the planned intervention will be explored. The results will inform the development of the implementation process. There will also be training sessions on site for each SPHC team between phase 1 and 2 to present results, and to discuss positive as well as negative comments received in phase 1.

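### The protocol plans to quantify selection of fitter patients with sociodemographic details alone, which measure fitness weakly at best

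*Protocol*

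**What the plan says.** In its Strengths and limitations section the Protocol describes a convenience sample identified by staff and states that "gatekeeping and sampling of only comparatively fitter patients cannot be ruled out completely". It hopes to reduce this through staff training and co-design, and then commits to a measurement: "We will compare the sociodemographic details of recruited patients with population data from the services to quantify this possible bias".

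The data analysis paragraph of substudy II makes the same commitment: "To judge the amount of sampling bias, the sociodemographic details of participants will be compared with population profiles of participating sites via descriptive statistics". The data listed for that substudy begin: "collected: age, gender, nationality (German or non-German), main diagnosis according to International Classification of Diseases, 10th Revision groups". Frequency of device use, device type and operating system follow. No item records performance status, phase of illness or prognosis.

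In substudy III, the Outcome measures section plans to extract from the records of the intervention and control groups "the number and severity of palliative symptoms and concerns and the steps taken by professionals for reducing the symptoms", as well as unplanned hospital admissions. The text does not link these data to the bias check.

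**The concern.** The bias is defined in terms of fitness, but the tool chosen to size it contains no measure of fitness. Two patients of the same age, gender and nationality can be at very different points in a terminal illness. A sample that matches the services on those variables could therefore look representative while being clearly less ill.

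The quantities at stake are those conditional on who was recruited, namely drop-out and completeness of eIPOS. Both are among the primary outcomes of substudy III and both plausibly depend on how ill patients are. The project exists to inform a cluster-randomised phase 3 trial, so false reassurance here would pass into its planning assumptions.

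**Working it through.** The protocol gives no figure for this check, so there is none to reproduce. The mismatch is a matter of reading; the arithmetic shows only how large the blind spot could be.

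**Inputs from the Protocol**
- Target for substudy III: 213 participants (Sample size calculation).
- Caseload of the participating teams: about 1,275 patients per year (same section).
- Target for substudy II: 50 participants.

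**Assumed inputs, not in the documents**
- D: the fitness difference of recruits, in SD units (0.5 to 1).
- r: the correlation of one sociodemographic variable with fitness (0 to 0.3).
- Selection acts through fitness only, and the relation is linear.

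**Step 1. Room for selection.** 213/1,275 = 16.7% of one year's caseload. The protocol does not fix a one-year recruitment window, and a low share may also reflect ineligibility or refusal. The figure shows that selection is possible, not that it occurs.

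**Step 2. What the check can see.** The expected shift in the sociodemographic variable is d = r × D. As an example, suppose 50% of the caseload but 80% of recruits are fitter:
- Standardised difference = 0.30 / sqrt((0.16 + 0.25)/2) = 0.30/0.453 = 0.66.
- At r = 0.2 the variable shows 0.2 × 0.66 = 0.13. At r = 0 it shows nothing.

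**Step 3. Would a formal test notice?** Compare 213 recruits with the other 1,275 − 213 = 1,062 patients, two-sided 5%. The standard error is sqrt(1/213 + 1/1,062) = 0.0751 SD, and the power is about Φ(d/0.0751 − 1.96). For d = 0.20: 0.20/0.0751 = 2.66, and Φ(0.70) = 0.76.

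| r | shift, D = 1 | flagged | shift, D = 0.5 | flagged |
|---|---|---|---|---|
| 0 | 0 | 5% | 0 | 5% |
| 0.1 | 0.10 | 27% | 0.05 | 10% |
| 0.2 | 0.20 | 76% | 0.10 | 27% |
| 0.3 | 0.30 | 98% | 0.15 | 52% |

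**Step 4. Simulation.** 213 of 1,275 patients were drawn with probability rising with fitness, 1,000 runs for each r. Recruits were on average about 0.93 SD fitter than the caseload.

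| r | mean visible shift (SD) | runs with shift below 0.1 SD |
|---|---|---|
| 0 | 0.00 | 89% |
| 0.1 | 0.09 | 55% |
| 0.2 | 0.19 | 9% |
| 0.3 | 0.28 | 0.1% |

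Even at r = 0.3, where a difference is almost always visible, it shows 0.28 of 0.93 SD, about 30%. Without knowing r, the visible shift cannot be converted into the size of the fitness bias.

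**Step 5. Substudy II.** With 50 participants, the standard error of a mean is 1/sqrt(50) = 0.14 SD. Shifts of 0.10 to 0.20 SD are then 0.7 to 1.4 standard errors, hard to tell from chance in a descriptive table.

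**The case against.** The strongest reply is that the protocol discloses the limitation, sets no threshold at which a clean comparison would rule the bias out, and already plans to collect severity data on non-recruited patients through the prospective control group. The variables in a descriptive table are often left to the analysis plan. The disclosure and the planned data count in the protocol's favour, and they make the remedy cheap. The appeal to an analysis plan does not succeed: the protocol itself fixes the comparison as sociodemographic and says it is there to quantify this bias.

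Other parts of the reply stand and limit the point:
- A reader might infer that this is the study's main bias. The text says only "A limitation of the study is its convenience sample based on staff identification of eligible patients in participating study sites"; it does not rank it.
- A reader might infer that the recruitment rate is distorted too. The total number of patients cared for will be extracted, and a rate on that denominator already includes gatekeeping.
- A reader might infer that the check will come out clean. That depends on r: with D = 1 a formal test would flag the shift in 76% of samples at r = 0.2 and 98% at r = 0.3. The check is weak, not empty.
- A reader might expect a comparison with the prospective controls to isolate gatekeeping. It cannot. Those controls include ineligible patients and patients who declined, while recruits must be judged well enough to take part and able to consent (Table 2). Recruits would be fitter even with no gatekeeping.
- Time to death or discharge is a tempting marker, but recruits must live and stay in care long enough to be approached, which lengthens it mechanically.

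**Conclusion.** The concern holds in this form: the protocol names sampling of fitter patients as a limitation and promises to quantify it with variables that measure fitness weakly at best. The mismatch follows from the text and needs no assumption. Its size does rest on assumptions. With recruits about 0.93 SD fitter, a sociodemographic variable would differ from the caseload by less than 0.1 SD in anything from 89% (r = 0) to 0.1% (r = 0.3) of samples, and would show at most about 0.28 SD over that range. D and r are not in the documents, and the calculation treats one variable at a time.

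The consequence falls mainly on drop-out and eIPOS completeness. How far these would move cannot be calculated, because the protocol does not relate either to fitness. For an exploratory feasibility study this is worth correcting, but it does not invalidate the design.

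**What to change.** **Substudy III.** Extend the bias check to compare recruited patients with the prospective control group on the symptom number and severity already planned for chart extraction, plus main diagnosis, alongside the sociodemographic data. Take all values at a common index point that exists for both groups, such as SPHC admission, and before any eIPOS use; patients who never use eIPOS have no eIPOS start date to anchor on. Report the difference as total selection, meaning eligibility, gatekeeping and refusal together. Attribute it to gatekeeping only where controls who met the eligibility criteria can be identified. Do not rest the statement on time to death or discharge unless it is measured from the common index point with survivorship handled.

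**Substudy II.** Add the diagnosis group, which is already collected, to the comparison, and state that sociodemographic details alone do not quantify selection on fitness.

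**Strengths and limitations.** Bring the sentence on quantifying the bias into line with the above.

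**Cost.** A little extra chart extraction (diagnosis, and symptom values at the index point) and some descriptive analysis. Chart-recorded symptom severity is an imperfect proxy for fitness, so the extended check will be better but not complete.
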